## **MATERIAL AND METHOD:**

- **Study design:** Randomized Controlled trial study is used.
- **Study Setting:** Department of Anesthesiology, Sindh institute of urology and transplantation (SIUT).
- **Duration:** 6 months after approval from ethical review committee of SIUT.
- **Sample size:** Based on the previous estimate of hypotension in sevoflurane group was found in 33% of patients and 8.8% in propofol infusion group with power of 80% & 5% level of significance. A total no of 86 patients will be part of study, out of which 43 will be selected for each group. [11]

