## **DATA COLLECTION PROCEDURE**

This study will be conducted after approval of ethical committee of SIUT. For research 86 patients will be selected for the elective ERCP. Pre-operative assessment will be taken such as history of patients, general physical examination, systematic examination, and laboratory investigations will be part of assessment. Patients will be divided in two groups based on agents used for the research study. Both the groups will be induced by injection midazolam 0.06 mg/kg and injection nalbuphine 0.1 mg/kg . Anesthesia will be maintained in.....

**Group A** Sevoflurane inhalation to achieve MAC Amnesia 0.25%.

**Group B** Propofol infusion at 50 ug/Kg/min.

When Ramsay Sedation Scale **5** is achieved than surgeon will be allowed to insert endoscope. Inj **Ketamine** 0.5mg/kg will be used for Rescue sedation .Upon arrival in operation theatre standard monitoring which includes pulse oxymeter (SPO2), noninvasive blood pressure (NIBP), electrocardiogram (ECG) electrodes will be applied, and baseline readings will be recorded. After that venous access will be secured on a non-dominant hand by 20G IV cannula, i/v fluid (R/L or N/S) will then be started by 8 ml/kg/h and O2 will be given by nasal mask at 4 L/min. All baseline parameters will be taken, after that readings will be taken at 5 min, 10 min, 15 min,20 min and so on till procedure ends.

Complications such as respiratory depression, coughing, gagging, nausea and vomiting will be recorded during the procedure and treated accordingly. If SpO2 goes down below 92% for more than 10 seconds or patient develops apnea, it will be considered oxygen desaturation.

It will be managed by O2 inhalation and supporting airway. A heart rate under 40beats per minute will be considered bradycardia and it will be managed by inj Atropine 10 ug/Kg I/V. Mean arterial pressure level that is lower than 60 mmHg or 20% less than the baseline will be regarded as hypotension and it will be managed by fluid bolus or vasopressors.

Complications such as respiratory depression, coughing, gagging, nausea and vomiting will be recorded and treated accordingly. After the procedure, patient will be awakened and shifted to HDU.

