#### **DATA ANALYSIS:**

For data analysis SPSS software will be used of version 22. Mean and standard deviation will be computed for variable such as age, height, BMI, RSS, HR, SBP, DBP and MAP at 0,1,3,5,10 min. For determining the differences in the hemodynamics mean unpaired “t” test will be used between groups. Categorical Variables such as gender, ASA and post op complications like gagging, PONV, Apnea and cough will be presented as frequencies and percentages.

Chi-square test will be followed and used between 2 groups, there proportion difference will be compared using P value

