## COMPLICATION DURING AND AFTER ERCP

DURING PROCEDURE	YES	NO
APNEA		
COUGH		
GAGGING		
POST-OPERATIVE NAUSEA AND VOMITING		

Ketamine used as Rescue Sedation	Yes	No	Number of doses given
----------------------------------	-----	----	-----------------------

RECOVERY TIME	MINUTES
---------------	---------

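### Blood pressure t-tests mix in readings taken after treatment of hypotension, which the plan expects far more often on sevoflurane, while hypotension itself, the sizing event, is not named for testing

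*Protocol*

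**What the plan says.** **Treatment.** In the Protocol's DATA COLLECTION PROCEDURE, a MAP below 60 mmHg or 20% under baseline is "regarded as hypotension and it will be managed by fluid bolus or vasopressors". For a heart rate under 40, "it will be managed by inj Atropine 10 ug/Kg I/V". Ketamine is the rescue sedative. All of this applies in both groups.

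**Expected frequency.** Under MATERIAL AND METHOD, the sample size is "Based on the previous estimate of hypotension in sevoflurane group was found in 33% of patients". The corresponding propofol figure is 8.8%; power is 80% at a 5% level. On numbers, the section says: "A total no of 86 patients will be part of study, out of which 43 will be selected for each group". No rate by arm is given for bradycardia or for ketamine.

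**Analysis.** The DATA ANALYSIS section lists HR, SBP, DBP and MAP at 0, 1, 3, 5 and 10 min, and says: "For determining the differences in the hemodynamics mean unpaired" t-tests will be used between groups. Chi-square is for categorical variables; those named are gender, ASA class, gagging, PONV, apnea and cough. Hypotension is not named. The SAP repeats this text. Neither document says what happens to readings taken after treatment.

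**Form.** The monitoring grid has a baseline row and then a row every 5 minutes to 60 minutes. There is no field for fluid bolus, vasopressor or atropine. The line "Ketamine used as Rescue Sedation" takes yes or no and a number of doses, without a time.

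**The concern.** The hypothesis is that propofol causes less haemodynamic instability than sevoflurane. Fluids and vasopressors are given to raise the pressure that the t-test then compares. If one arm needs them more often, its later mean is lifted more, and the gap between arms narrows because the less stable arm was treated. A real difference in stability could then be reported as small or absent.

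The event that would show the difference directly, and on which the trial was sized, is not named for any test. The form also gives only partial means of sorting treated from untreated readings afterwards.

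**Working it through.** **Inputs from the Protocol:** hypotension 33% (sevoflurane) and 8.8% (propofol); 80% power; 5% level (sidedness not stated, two-sided assumed); 43 per arm; trigger MAP below 60 mmHg or 20% under baseline.

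**Assumptions, because the documents give no figures:** the rise in MAP produced by treatment (r), the share of eventual events already treated at the analysed reading (f), baseline MAP, and the SDs.

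**1. The plan's own figure.** Pooled proportion = (0.33 + 0.088)/2 = 0.209.

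n = [1.96 x √(2 x 0.209 x 0.791) + 0.842 x √(0.33 x 0.67 + 0.088 x 0.912)]² / 0.242² = 43.1 per arm.

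This rounds up to 44, and power at 43 is 79.9%. The stated 43 is reproduced, so the two rates really are the design assumption.

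**2. Patients treated for hypotension.** 43 x 0.33 = 14.2 and 43 x 0.088 = 3.8. The ratio is 0.33/0.088 = 3.75.

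**3. Narrowing of the MAP difference at a reading after treatment.** Narrowing = f x (0.33 - 0.088) x r.

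| r (mmHg) | f = 1 | f = 0.5 |
|---|---|---|
| 5 | 1.2 | 0.6 |
| 10 | 2.4 | 1.2 |
| 15 | 3.6 | 1.8 |
| 20 | 4.8 | 2.4 |

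**4. Which planned tests are exposed.** The 0-min reading precedes rescue. If hypotension is found at the scheduled 5-minute readings, the reading that triggers treatment is itself untreated, so a fall first found at 5 min affects only the 10-min test. The 1- and 3-min times have no row on the form. Readings continue to the end of the procedure, where f would be largest, but the analysis section names no time after 10 min.

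**5. Illustration of size.** Assume baseline MAP 95 mmHg (SD 12), percent change in MAP normal with SD 12, and r = 15 mmHg. Set the arm means so that 33% and 8.8% fall by more than 20%: -20 + 0.440 x 12 = -14.7% and -20 + 1.353 x 12 = -3.8%. The untreated difference is 0.913 x 12% x 95 = 10.4 mmHg. Simulated with 43 per arm, t-test on raw MAP:

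| Events treated by the reading | Difference (mmHg) | Power |
|---|---|---|
| none | 10.4 | about 85% |
| one third | 9.2 | about 79% |
| half | 8.6 | about 75% |
| all | 6.7 | about 60% |

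In the same simulation a chi-square on any hypotension has about 82% power whatever the lift. That is slightly above the 79.9% in step 1 because the 60 mmHg limb adds a few events. With all events treated, SD of change 10 to 15% and lift 10 to 20 mmHg, the untreated difference of 8.7 to 13.1 mmHg falls to 3.8 to 10.6 mmHg, and power falls from 79-91% to roughly 28-84%.

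**The case against.** **The target may be the regimen with its rescue.** If the question is how pressures compare when each drug is given with its rescue as needed, the t-test is a valid comparison. This stands, but the plan does not say so, and its hypothesis asks which drug causes less instability.

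**Few planned tests are exposed.** This largely stands, as step 4 shows. The documents do not define time zero or rule out extra readings, so it is the likely reading, not a certain one.

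**The simulated loss is an upper case.** This stands. The 33% and 8.8% are proportions of patients with no time attached, and the full loss needs every event to be treated before the analysed reading. A test on change from baseline would lose less: under similar assumptions its untreated power is 98-99%. The plan, however, describes raw means at each time.

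**Treated readings can be recovered from the grid.** Partly. The triggers are numeric and MAP and HR are recorded every 5 minutes, so readings after a qualifying value can be flagged. Falls between readings, the treatment actually given, and the timing of ketamine cannot be recovered.

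**Hypotension may be covered already.** The categorical list is given by example and hypotension can be derived from the grid. Even so, it is not named, and it has no box on the form.

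**A stronger reading that a reader might infer** is that all rescue, including atropine and ketamine, biases both blood pressure and heart rate towards no difference. The documents do not support this. If ketamine raised MAP by 10 mmHg (assumed), use of 30% on sevoflurane and 10% on propofol would narrow the difference by (0.30 - 0.10) x 10 = 2 mmHg; the reverse pattern would widen it by 2 mmHg. Atropine would narrow a heart-rate gap only if given more often in the arm with the lower rate. The effect of hypotension treatment on heart rate depends on an agent that the Protocol does not name.

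**Conclusion.** The point holds for blood pressure and for treatment of hypotension. On the plan's own rates that treatment is unequal between arms, and it pulls later MAP differences towards zero by up to 2.4 mmHg per 10 mmHg of lift, less if some events have not yet been treated. The direction of any effect of ketamine or atropine, and of any effect on heart rate, is open.

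The fall in power from about 85% to about 60%, or to about 75% if half the events have been treated, rests on assumed values and is not a property of this plan. Nor is the t-test invalid in itself: the defect is an unstated target, combined with the sizing event being left out of the named tests. The correction is cheap and should be made, but it does not put the trial as a whole in question.

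**What to change.** 1. In the Protocol's DATA ANALYSIS section and the SAP, name hypotension at any time from baseline to the end of the procedure as the main test of haemodynamic instability, by chi-square between arms. Use the Protocol's existing definition and count any patient treated for hypotension as an event, so that falls between readings are included. The first fall comes before its own treatment, so that treatment cannot dilute this measure, although ketamine given earlier could still influence it.
2. Add to the form the type and clock time of each fluid bolus, vasopressor, atropine and ketamine dose. A tick in a 5-minute row would not show whether the rescue came before or after that row's reading.
3. Report each rescue by arm. Present the time-point means as secondary, stated to compare each regimen with its rescue as given.

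Two other remedies are best avoided. The lowest MAP before first rescue is cut short more often on sevoflurane. Dropping readings after ketamine selects on an event that follows randomisation.

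**Cost:** a few form fields, a few sentences, and submission of the revised protocol to the ethics committee, as its approval letter requires. No extra patients or procedures are needed and no clinical rule changes. The small downside is that the time-point t-tests become secondary.

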#### **DATA ANALYSIS:**

For data analysis SPSS software will be used of version 22. Mean and standard deviation will be computed for variable such as age, height, BMI, RSS, HR, SBP, DBP and MAP at 0,1,3,5,10 min. For determining the differences in the hemodynamics mean unpaired “t” test will be used between groups. Categorical Variables such as gender, ASA and post op complications like gagging, PONV, Apnea and cough will be presented as frequencies and percentages.

Chi-square test will be followed and used between 2 groups, there proportion difference will be compared using P value

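### Haemodynamic means are compared by unadjusted t-tests with no variable or time ranked, although every patient's baseline is recorded and the outcome used for sizing is not named as primary

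*Protocol*

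**What the plan says.** The Data Analysis section of the protocol, repeated almost word for word in the SAP, has one inferential sentence for haemodynamics: "For determining the differences in the hemodynamics mean unpaired “t” test will be used between groups". It names no primary variable, primary time, summary measure, baseline adjustment or rule for multiple tests.

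The only analysis times appear in the descriptive sentence before it, which covers "RSS, HR, SBP, DBP and MAP at 0,1,3,5,10 min". The Data Collection Procedure has a different schedule: "All baseline parameters will be taken, after that readings will be taken at 5 min, 10 min", and so on to the end of the procedure. The recording form (Performa) matches that schedule, with a baseline row and then rows every 5 min to 60 min. It has no 1 or 3 min row.

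The only stated use of the baseline is in an event definition: "Mean arterial pressure level that is lower than 60 mmHg or 20% less than the baseline will be regarded as hypotension".

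The sample size rests on that event: "previous estimate of hypotension in sevoflurane group was found in 33% of patients and 8.8% in propofol infusion group", with 80% power, 5% significance and 43 per group. Neither document calls hypotension primary. The categorical variables are introduced by example, the complications among them as "post op complications like gagging, PONV, Apnea and cough will be presented as frequencies and percentages". A general sentence then applies the chi-square test to proportions in the two groups.

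**The concern.** Two things are at stake.

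- **Precision.** Part of the spread in a later blood pressure or heart rate reading is explained by where that patient started. An unadjusted t-test leaves this in the error term, so the intervals are wider than the collected data allow.
- **Interpretation.** The hypothesis predicts more stable haemodynamics with propofol but names no variable, time or measure. With several unranked tests, a single small p-value could be read as support. Meanwhile the outcome that justified 86 patients is not marked as the one that decides the question.

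**Working it through.** **Inputs from the documents:** 43 per arm; hypotension 33% v 8.8%; 80% power; 5% significance (two-sided assumed, as the sidedness is not stated); four haemodynamic variables; listed times 0, 1, 3, 5 and 10 min; collection at baseline and then every 5 min. **Not given, so assumed:** the correlation r between baseline and later readings, and the correlations across times and variables.

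**1. The plan's own sample size.** Pooled formula, with mean proportion (0.33 + 0.088)/2 = 0.209:

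n = [1.960 × √(2 × 0.209 × 0.791) + 0.842 × √(0.33 × 0.67 + 0.088 × 0.912)]² / 0.242² = (1.127 + 0.462)² / 0.0586 = 43.1 per arm.

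This agrees with the stated 43 to within rounding up. So the trial is sized on a proportion, not on a mean.

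**2. Power for hypotension by version of the test.** Summing exact binomial probabilities over all 2×2 tables with 43 per arm at 33% v 8.8%:
- uncorrected chi-square: 82.5%
- chi-square with continuity correction: 72.4%

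The plan does not say which version is meant, and only the first keeps the planned 80%.

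**3. Precision at a single time.** The unadjusted half-width is t(84) × √(2/43) = 1.989 × 0.2157 = 0.429 SD. ANCOVA multiplies the residual variance by 1 − r².

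| Assumed r | Variance factor | Half-width (SD) | Narrower by | Equivalent n per arm, 43/(1 − r²) |
|---|---|---|---|---|
| 0.3 | 0.91 | 0.409 | 5% | 47 |
| 0.5 | 0.75 | 0.371 | 13% | 57 |
| 0.7 | 0.51 | 0.306 | 29% | 84 |

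Estimating the slope costs one degree of freedom and changes these half-widths by about 0.001 SD.

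**4. Chance findings.** Only 5 and 10 min are both listed for analysis and collected after baseline. Assuming that the tests are confined to those times gives 4 variables × 2 times = 8 tests. Simulated null trials, 43 per arm, with constant correlation over time crossed with constant correlation between variables:

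| Correlation over time, between variables | At least one p<0.05 | At least one in one chosen direction per variable |
|---|---|---|
| 0.5, 0.3 | 30% | 15% |
| 0.7, 0.5 | 25% | 12% |
| 0.9, 0.8 | 16% | 8% |

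A weaker setting (0.3, 0.3) gives 31% and 16%. A fair reading is about 16-30% and 8-16%, against 5% and 2.5% for one pre-specified two-sided test.

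**The case against.** **The t-tests are valid.** This stands. Randomisation makes each unadjusted comparison valid, and stated power concerns a proportion, so it is unaffected. Baseline adjustment is a gain in efficiency whose size depends on an unknown r.

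**Hypotension is already covered.** This largely stands. A reader might infer that the sized outcome has no test or cannot be recovered from the form. The documents do not support that. The variable lists are illustrative, the chi-square sentence is general, hypotension is a defined yes/no event, and it can be derived from the form's MAP column. What remains is that it is not named as primary or listed, and that the chi-square version is open.

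**The error rates can be made to look worse.** Eight independent tests would give 1 − 0.95⁸ = 34%, but readings repeat within patients and MAP is tied to SBP and DBP, so independence is not credible. Testing all 12 post-baseline rows of the form (48 tests) would give more still. The plan lists times only to 10 min, however, and that count needs every procedure to last 60 min. A simulation that builds MAP from SBP and DBP, with assumed SDs and correlations, gives 18-24% in any direction and 9-12% in one. Both lie inside the ranges above.

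**A tilt towards propofol.** A reader might infer that the plan is biased in propofol's favour. It is not: chance results fall equally either way. Counting only favourable ones needs a chosen direction for each variable, which the hypothesis does not give; for heart rate, either direction could count as instability.

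**Two baselines.** The procedure text says "baseline readings will be recorded. After that venous access will be secured" and mentions baseline again after fluids and oxygen. That text is not in time order and the form has one baseline row, so this may be loose drafting. It is enough to name the row used.

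**Conclusion.** The point holds as a recommended improvement, not as an error that invalidates the trial. It is clear from the text alone, with no assumption, that no variable or time is ranked, that the recorded baseline is unused in the comparison of means, that the sized outcome is not declared primary, and that the listed and collected times disagree.

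The sizes do rest on assumptions. The precision gain runs from slight (5% narrower at r = 0.3) to substantial (29% at r = 0.7). The chance of a spurious result is about three to six times that of a single pre-specified test, given eight tests and the assumed correlations. Whether anyone would headline such a result is a matter of reporting that the documents cannot settle.

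**What to change.** 1. Replace the t-test sentence in both documents with one model: each post-baseline HR, SBP, DBP and MAP value is analysed by ANCOVA on group and the patient's own value from the form's baseline row, reported with 95% CIs. Do not test baseline between groups.
2. Name as primary the proportion of patients with hypotension, as the Data Collection Procedure already defines it, at any post-baseline reading recorded on the form. Derive it from the MAP column and compare it by the uncorrected chi-square test, with the difference in proportions and its 95% CI. Anchoring on the baseline row avoids relying on a 0 min that the documents do not define.
3. Label the comparisons of haemodynamic means as supportive or exploratory.
4. Reconcile the listed analysis times (0, 1, 3, 5, 10 min) with the collection times (baseline, then every 5 min) before any group comparison is seen.

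**Cost.** No new readings and the same software, with slightly more analysis work. The ethics approval letter filed with the SAP requires a revised protocol to be approved before changes are implemented, so a resubmission is needed. Single-time p-values could no longer be headlined. One limit remains: longer procedures give more readings at which an event can be seen, and the documents do not show whether the 33% and 8.8% were counted in this way.

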## PERFORMA

GROUP A  GROUP B 

CASE#	
DATE	
Serial #	
AGE	YEARS
SEX	MALE    FEMALE
WEIGHT	KG
HEIGHT	Cm
MALAMPATI SCORE	
ASA	
BMI	Kg/m 

Time in min	Haemodynamic Monitoring			Respiratory Monitoring			Sedation monitoring	
	HR b/n	SBP mmHg	DBP mmHg	MAP mmHg	SpO2%	R/R/min	END TIDAL CO2	Ramsay sedation score
Base line								
5 min								
10 min								
15 min								
20 min								
25 min								
30 min								
35 min								
40 min								
45 min								
50 min								
55 min								
60 min								

### Ramsay Sedation Scale

1	Patient is anxious and agitated or restless, or both
2	Patient is co-operative, oriented, and tranquil
3	Patient responds to commands only
4	Patient exhibits brisk response to light glabellar tap or loud auditory stimulus
5	Patient exhibits a sluggish response to light glabellar tap or loud auditory stimulus
6	Patient exhibits no response
Source: Ramsay MA, Savege TM, Simpson BR, Goodwin R. Controlled sedation with alphaxolone - alphadalone . Br Med J. 1974;2:656-9.	

## COMPLICATION DURING AND AFTER ERCP

DURING PROCEDURE	YES	NO
APNEA		
COUGH		
GAGGING		
POST-OPERATIVE NAUSEA AND VOMITING		

Ketamine used as Rescue Sedation	Yes	No	Number of doses given
----------------------------------	-----	----	-----------------------

RECOVERY TIME	MINUTES
---------------	---------

Comparison between inhalational anesthetic (sevoflurane) and intravenous anesthetic (propofol infusion) for maintenance of sedation during Endoscopic retrograde cholangiopancreatography

Principle investigator

[name]

Senior Lecturer

Department of Anesthesiology SIUT Karachi

Dated: 01-07-2021

DATA ANALYSIS:

For data analysis SPSS software will be used of version 22. Mean and standard deviation will be computed for variable such as age, height, BMI, RSS, HR, SBP, DBP and MAP at 0,1,3,5,10 min. For determining the differences in the hemodynamics mean unpaired “t” test will be used between groups. Categorically Variables such as gender, ASA and post op complications like gagging, PONV, Apnea and cough will be presented as frequencies and percentages.

Chi-square test will be followed and used between 2 groups, there proportion difference will be compared using P value

(Note: This plan is a part of synopsis which we have uploaded on NCT form)

Monday, August 30, 2021
ERC Number: 325

Approval No: SIUT-ERC-2021/A-325

Approval Issued: August 30, 2021

[name]
Department of Anesthesia, SIUT

Re: Project Title “Comparison between inhalational anesthetic (sevoflurane) and intravenous anesthetic (propofol infusion) for maintenance of sedation during Endoscopic retrograde cholangiopancreatography.”

[figure not shown]
Dear [name],

Thank you for submitting the above referenced protocol to the SIUT-Ethical Review Committee (ERC). ERC finds that this protocol raises no ethical concerns. Approval is granted and you may commence your research. According to SIUT-ERC requirements, the ERC approval number should be clearly printed and visible on all consent forms used in the study.

Please note that this approval is valid for one year and relates to the ethical content of the study only. If you make any changes to the protocol during the period of this approval, you must submit a revised protocol to the SIUT-ERC for approval before implementing the changes.

SIUT-ERC requires a follow up from all researchers about the status of the approved research at the completion of one year from the date of issuance. You are also expected to comply with this practice.

Yours Sincerely,

[name], DABIM, DABP, DAB Nephrology
Professor and In charge Pediatric Nephrology,
Co-Chair, SIUT-Ethical Review Committee (SIUT-ERC)
